### 9.2.2. CMH - categorical endpoints

Categorical efficacy endpoints will be analyzed using the Cochran-Mantel-Haenszel (CMH) test. The CMH test will compare treatment groups (crinecterfont 100 mg bid vs. placebo) and will include the stratification factors used in the randomization.

An example of the SAS software code is provided below. Note that the PROC FREQ statements shown in this section will be accompanied by additional statements to create and output the required statistics.

PROC FREQ;

TABLES SEX\*TRTP\*GC\_TYPE\*GC\_DOSE\*RESPONSE / CMH;

RUN;

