The second key secondary endpoint is the achievement of a reduction in glucocorticoid daily dose to physiologic levels ($\leq 11 \text{ mg/m}^2/\text{day}$ hydrocortisone equivalents adjusted for BSA) at Week 24, while Week 24 androstenedione is adequately controlled at $\leq 120\%$ of baseline or $\leq \text{ULN}$ for age and sex. Androstenedione levels used to assess adequate control is as described for the primary endpoint above. The primary analysis of this endpoint will be performed using a Cochran-Mantel-Haenszel (CMH) test. The CMH test will compare treatment groups and will include the stratification factors used in the randomization. Subjects whose androstenedione levels at Week 24 are not controlled will be considered non-responders. Subjects who are missing their glucocorticoid dose or all androstenedione data at Week 24 will have their data imputed through a multiple imputation procedure. Missing data will be imputed for subjects in the crinecerfont treatment group using retrieved data (ie, observed data from subjects who discontinued study drug) in the crinecerfont treatment group, provided there is sufficient retrieved data. Otherwise, missing data will be imputed using observed data from subjects in the placebo treatment group. For subjects in the placebo treatment group, missing data will be imputed using observed data from subjects in the placebo treatment group. This analysis will be performed using the FAS.

Additional key secondary endpoints are the changes from baseline in HOMA-IR, weight, and fat mass at Week 24, which will be analyzed using an ANCOVA model. The model will include treatment group, corresponding baseline values, and stratification factors used in the randomization. Subjects who are missing data at Week 24 will have their data imputed through a multiple imputation procedure using the retrieved data method as described for the first key secondary endpoints above. This analysis will be performed using the FAS.

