### 9.1. Multiple Comparisons and Multiplicity

The testing procedure described below will be used to control the familywise Type I error rate for the primary and key secondary endpoints (Figure 1). The promising zone method as planned in this study was shown to not inflate the type I error, as described in the simulation report attached to the Adaptation Plan. All significance levels noted below are 2-sided. All other p-values will not be adjusted for multiplicity and should be considered as nominal p-values.

- The primary endpoint will be tested using a significance level of 0.05.
- If the primary endpoint is statistically significant, then the first 2 key secondary endpoints will be tested using an unequal allocation of significance levels. The change from baseline at Week 4 in androstenedione will be tested using a significance level of 0.02. The achievement of a reduction in glucocorticoid daily dose to physiologic levels ( $\leq 11 \text{ mg/m}^2/\text{day}$  hydrocortisone equivalent adjusted for BSA) will be tested using a significance level of 0.03.
- The family of remaining key secondary endpoints will be tested using the Holm procedure (Holm, 1979). The significance level for this family of endpoints will be dependent on whether the first 2 key secondary endpoints are statistically significant (Wiens, 2003). If both are statistically significant, then the significance level for this family of endpoints will be 0.05. If only one is statistically significant, then the significance level for that endpoint will be used for this family of endpoints. If neither is significant, then this family of endpoints will not be tested for statistical significance. However, nominal p-values will be produced.

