#### **9.4.2. Physiologic Glucocorticoid Daily Dose Responder Analysis**

The second key secondary endpoint is the achievement of a reduction in glucocorticoid daily dose to physiologic levels ( $\leq 11 \text{ mg/m}^2/\text{day}$  hydrocortisone equivalent adjusted for BSA) at Week 24, while Week 24 androstenedione is adequately controlled at  $\leq 120\%$  of baseline or  $\leq \text{ULN}$  for age and sex. The selection of the baseline and Week 24 androstenedione values used to assess control for this endpoint is the same method as is used for the primary endpoint (and described in Section 6.3.3). The primary analysis of this endpoint will be performed using a CMH test as described in Section 9.2.2. The CMH test will compare treatment groups and will include the stratification factors used in the randomization. If the model fails to converge due to a small number of observations within a cell, stratification levels may be collapsed to allow for model convergence. Subjects whose androstenedione levels at Week 24 are not controlled will be considered non-responders. For subjects who are missing glucocorticoid dose, androstenedione, or both at Week 24, the multiply-imputed datasets from the primary endpoint will be used to determine response.

Descriptive statistics will be presented by treatment group for the number and percentage of subjects classified as responders and non-responders at each postbaseline visit. For the Week 24 visit, the treatment difference and p-value from the CMH analysis will also be displayed.

A tipping point sensitivity analysis of the achievement of reduction in physiologic glucocorticoid daily dose at Week 24 will be performed to assess the robustness of the missingness assumptions as was described for the primary endpoint in Section 9.3.3. The implementation procedure for the tipping point analysis is described in Appendix 16.6 for this key secondary efficacy endpoint.

A complete-case sensitivity analysis will also be performed to test the robustness of the multiple imputation procedure. The CMH analysis for the physiologic glucocorticoid daily dose endpoint will be repeated using only subjects with observed data at Week 24. Subjects who are missing the Week 24 secondary endpoint will be excluded from the analysis.

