#### **9.5.5. Menstrual Regularity**

Menstrual regularity at Week 24 (in female subjects of childbearing potential who are not on hormonal or intrauterine device contraceptives) is a secondary endpoint. Subjects meeting these criteria were asked to input the dates for which they were assessing their menstrual cycle as well as the amount of flow (light [spotting], medium [normal flow], heavy [heavy flow with flooding or clotting]). For the purposes of this analysis, a menstrual cycle will be defined as two consecutive calendar days with any amount of flow. Menstrual cycle regularity is defined as a menstrual cycle every 21-35 days, translating to approximately 4 to 8 menstrual cycles from baseline to Week 24. The number and percentage of subjects meeting the definition for regular menstrual cycle at Week 24 will be summarized by treatment group. This summary will be stratified based on menstrual cycle regularity at study entry (as collected on the CAH medical history eCRF, “Do menstrual cycles typically occur every 21-35 days?”). This endpoint will be analyzed using a CMH test as described in Section 9.2.2. The CMH test will compare treatment groups and will include the stratification factors used in the randomization (with the exception of sex) as well as menstrual cycle regularity at study entry. The p-value from the CMH analysis will also be displayed in a table.

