## 16.6. Implementation of Tipping Point Analysis for the Key Secondary Endpoint: Physiologic Glucocorticoid Daily Dose Responder

This section will discuss the tipping point analysis for physiologic glucocorticoid daily dose responders which is also a key secondary endpoint as described in Section 9.4.2. This key secondary endpoint is defined as the achievement of a reduction in glucocorticoid daily dose to physiologic levels ( $\leq 11 \text{ mg/m}^2/\text{day}$  hydrocortisone equivalent adjusted for BSA) at Week 24, while Week 24 androstenedione is adequately controlled at  $\leq 120\%$  of baseline or  $\leq \text{ULN}$  for age and sex.

A tipping point sensitivity analysis will be performed to assess the robustness of the missing data assumptions for the glucocorticoid daily dose at Week 24. The following steps will be taken to implement the tipping point analysis for this key secondary endpoint:

- 1) For the 100 imputed datasets created (as described in Section 16.1), if a subject was originally missing the Week 24 value (i.e., missing the glucocorticoid daily dose at Week 24), add *delta* (see rules below) to the imputed Week 24 value. Calculate the change from baseline to Week 24 for all subjects as applicable:
  - If the Week 24 endpoint value is non-missing: change from baseline = (Week 24 value – baseline value).
  - If the Week 24 endpoint value is missing and the subject is in either the crinecerfont treatment group or placebo treatment group: change from baseline = (Week 24 delta-adjusted imputed value – baseline value).
- 2) If the subject does not have androstenedione control at Week 24 (as defined in the primary endpoint) then the change from baseline will be set to 0 prior to the analysis of the delta-adjusted imputed datasets.
- 3) Determine if each subject is a responder or a non-responder. Analyze the categorical data at Week 24 for the values in each of the 100 imputed datasets using the Cochran-Mantel-Haenszel (CMH) test. The CMH test will compare treatment groups (crinecerfont 100 mg bid vs. placebo) and will include the stratification factors used in the randomization. Use PROC MIANALYZE to combine the results and obtain the p-value.
- 4) If the p-value in the previous step was not significant (i.e.,  $>0.05$ ), then no additional analyses are needed. If the p-value was significant, repeat the previous steps using the

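### The only CMH code in the SAP (Section 9.2.2) crosses baseline dose stratum, not treatment, with response, and so contradicts the test described in the text

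*SAP*

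**What the plan says.** The text of SAP Section 9.2.2 defines the test correctly: "The CMH test will compare treatment groups (crinecterfont 100 mg bid vs. placebo) and will include the stratification factors used in the randomization". Protocol Section 13.6.1.3 agrees ("The CMH test will compare treatment groups and will include the stratification factors used in the randomization"), and SAP Sections 9.4.2 and 16.6 repeat the same aim.

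The code follows, introduced by "An example of the SAS software code is provided below". The operative line is "TABLES SEX\*TRTP\*GC\_TYPE\*GC\_DOSE\*RESPONSE / CMH". It is the only CMH code in the SAP, and no other section gives a different variable order.

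The section matters because SAP Section 9.4.2, on the physiologic-dose responder endpoint, refers to it directly: "The primary analysis of this endpoint will be performed using a CMH test as described in Section 9.2.2". SAP Section 9.1 tests that endpoint at 0.03 and makes the alpha for the three remaining key secondary endpoints depend on it and on Week 4 androstenedione: "If only one is statistically significant, then the significance level for that endpoint will be used for this family of endpoints".

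**The concern.** The line pairs the wrong variables. Treatment sits second in the list, among the stratification factors, and the variable next to response is the two-level dose stratum (below 20 versus 20 mg/m²/day or more). Run literally, the test asks whether subjects who start on a higher dose respond differently from those who start lower, within each arm. It says nothing about crinecerfont versus placebo.

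The error is easy to miss. The line is valid syntax, runs without an error message and returns a p-value of ordinary appearance. The endpoint also makes a spurious result plausible: response means reaching 11 mg/m²/day or less, and subjects starting at 20 or more have further to fall.

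A wrong result would affect the responder claim itself and, through the testing procedure, the alpha available for HOMA-IR, weight and fat mass. The other analyses that cite Section 9.2.2 (SAP Sections 9.5.5, 9.5.6, 9.6.1 and 9.6.9) carry nominal p-values only.

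**Working it through.** **Structure of the request.** `GC_DOSE` is the categorical stratification factor: the ANCOVA example in SAP Section 9.2.1 lists it as a class variable separate from the baseline covariate, and SAP Section 3.1 gives its two levels.

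| | Strata | Table tested |
|---|---|---|
| As printed | sex × treatment × GC type (2×2×3 = 12) | GC dose stratum × response |
| As the text says | sex × GC type × GC dose stratum (2×3×2 = 12) | treatment × response |

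No positional reading pairs treatment with response: the first two variables are sex and treatment, the last two are dose stratum and response. In the printed order every stratum contains a single arm, so a treatment effect cannot contribute to the statistic.

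**Statistic.** For stratum *s* of size *n*, with row total *r*, column total *c* and cell count *a*:

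Q = [Σ(a − rc/n)]² / Σ[r(n−r)c(n−c) / (n²(n−1))], referred to chi-square on 1 df.

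This formula matched a library implementation for both orders. In one simulated dataset generated with response rates of 60% and 15%, the printed order gave Q = 1.70 (p = 0.19) and the intended order gave Q = 35.5 (p = 2.6 × 10⁻⁹).

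**Illustrative rejection rates.** From the documents: 165 subjects at 2:1 and alpha 0.03. The documents give no response rates or stratum shares, so these are assumptions: sex 50:50; GC type 55/33/12%; 35% or 50% of subjects in the upper dose stratum; logistic response; 2:1 block randomisation within strata. Each scenario used 10,000 trials. The treatment effect is 50% versus 20%; no effect is 30% in both arms. Cells show intended / printed order, in percent.

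| Scenario | Dose log-odds ratio | 35% in upper stratum | 50% in upper stratum |
|---|---|---|---|
| Treatment effect only | 0 | 95.8 / 2.9 | 95.7 / 2.9 |
| Neither effect | 0 | 2.9 / 3.1 | 3.1 / 3.1 |
| Dose effect only | −0.5 | 2.9 / 19.0 | 3.3 / 22.7 |
| Dose effect only | −1.0 | 2.7 / 66.2 | 2.9 / 74.9 |
| Dose effect only | −1.5 | 3.1 / 95.2 | 2.7 / 98.2 |
| Both effects | −0.5 | 95.5 / 21.4 | 95.4 / 23.8 |
| Both effects | −1.0 | 94.6 / 71.0 | 94.2 / 76.7 |
| Both effects | −1.5 | 94.5 / 97.3 | 93.6 / 98.6 |

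The similar rates in the last row are coincidental, because the two orders test different hypotheses. A second run with other assumptions (30% in the upper stratum, unstratified 110:55 allocation, 5,000 trials) gave 93.9 / 3.0 for a treatment effect only and 3.2 / 94.0 for a dose effect only (45% versus 15% response).

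**Alpha passed on.** Three endpoints remain in the Holm family, so the first step is the family alpha divided by 3.

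| Week 4 androstenedione | Responder significant | Responder not significant |
|---|---|---|
| Significant | 0.05; first step 0.05/3 = 0.0167 | 0.02; first step 0.02/3 = 0.0067 |
| Not significant | 0.03; first step 0.03/3 = 0.0100 | family not tested |

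**The case against.** The planned hypothesis is not in doubt. Four sections state it in words and agree, and the code is offered as an example. SAP Section 14 requires each program to be verified and the output to be reviewed independently.

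The line also cannot be the complete production program. Section 9.4.2 calls for a treatment difference beside the p-value, for analysis of multiply imputed datasets, and for possible collapsing of strata. Other sections change the strata: Section 9.5.5 applies the randomisation factors "with the exception of sex) as well as menstrual cycle regularity at study entry". A programmer has to adapt the line and may notice the order in doing so. The rejection rates describe literal execution under assumed rates and omit imputation and collapsing. They are not the error rate of the trial.

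Most of this stands, and it limits the weight of the point. It does not correct the line. Processing by imputation, pooling and output statements can all be added without touching the variable order, and a treatment difference can be produced separately. Section 14 leaves open whether verification is by independent programming or by review of logs. The log of this line would be clean, and a second programmer working from the same example could repeat the order.

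**Conclusion.** The concern holds. The printed request contradicts the test stated in SAP Sections 9.2.2, 9.4.2 and 16.6 and in Protocol Section 13.6.1.3, and nothing in either document corrects it. That conclusion rests only on the order of the variables, not on any assumed rate.

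If the line were run as printed, a true treatment effect alone would be detected at about the nominal 3% rate instead of about 96% (assuming 50% versus 20%). A baseline-dose association alone would produce rejection in 19% to 98% of trials for log-odds ratios of −0.5 to −1.5. Whether it would be run that way cannot be known from the documents, and the correct text makes it less likely. The point should be fixed because this is the SAP's sole code for an alpha-controlled endpoint that also helps set the alpha for three others.

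**What to change.** Replace the line in SAP Section 9.2.2 with

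`TABLES SEX*GC_TYPE*GC_DOSE*TRTP*RESPONSE / CMH;`

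and state that treatment and response must always be the last two variables. Where a section drops sex (9.5.5, 9.5.6, 9.6.1) or adds a factor (menstrual regularity at entry in 9.5.5), only the leading strata change. Record the correction in the SAP Document History, and confirm the variable order in the production programs for Sections 9.4.2 and 16.6.

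The cost is one line in a versioned SAP correction and a short program check. No protocol amendment, new data or additional subjects are needed.

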**Population-level summary:** The least-squares mean treatment difference for this endpoint will be estimated using an ANCOVA model. Missing data will be imputed using the multiple imputation procedures defined in Section 16.1.

### 9.3.2. Primary Efficacy Analysis

The primary efficacy endpoint is the percent change from baseline in glucocorticoid daily dose (in hydrocortisone equivalents adjusted for BSA [mg/m^2/day]) at Week 24, while Week 24 androstenedione is adequately controlled at  $\leq 120\%$  of baseline or  $\leq \text{ULN}$  for age and sex.

Glucocorticoid daily dose will be calculated at baseline (as defined in Section 6.3.1) and at Week 24 using the doses reported on the glucocorticoid medications eCRF (see details in Section 6.7 regarding mapping of the glucocorticoid medication to Week 24). Glucocorticoids other than hydrocortisone will be converted to hydrocortisone equivalents using the equivalency factors defined in Appendix A of the study protocol and Section 16.3. BSA will be calculated using the height from the screening visit and weight from the Day 1 visit, computed using the DuBois formula (Section 7.3). If glucocorticoid dosing alternates over the course of two consecutive days, then the average of the glucocorticoid dose on those days will be used to calculate the glucocorticoid daily dose. If glucocorticoid dosing alternates between weekdays and weekends (or another weekly regimen that varies by day of the week), then the average daily dose will be calculated as the sum of the glucocorticoid doses over the 7-day period divided by 7.

Baseline androstenedione will be defined as the Day 1 post-morning glucocorticoid dose androstenedione value. Further details of the derivation of this baseline value are described in Section 6.3.3.

Subjects who have a decrease in glucocorticoid daily dose but do not meet the definition of androstenedione control at Week 24 will be considered to have a zero percent change from baseline in the glucocorticoid daily dose at Week 24. Any increases from baseline in glucocorticoid daily dose will be reported as such, regardless of androstenedione control.

Subjects who are missing Week 24 glucocorticoid dose data or all Week 24 androstenedione levels will have their data imputed through the multiple imputation procedures described in Section 16.1.

The primary analysis of the primary endpoint will be performed using the CHW test statistic (Cui, Hung, Wang, 1999) comprising test statistics from stage 1 of the trial (the interim dataset), and stage 2 of the trial (the remaining part of the trial). Each test statistic will be generated using an analysis of covariance (ANCOVA) model, as described in Section 9.2.1. If the total sample size was increased in a data-dependent manner as a result of the interim analysis, the primary analysis of the primary endpoint will be performed using the CHW test statistic, as proposed by Cui, Hung, and Wang (1999) and independently by Lehmacher and Wassmer (1999), to determine statistical significance. The CHW test statistic is a weighted test statistic comprised of test statistics from stage 1 of the trial (the interim dataset) and stage 2 of the trial (the remaining part of the trial). Each test statistic will be generated using an ANCOVA model, as described in Section 9.2.1. The independent increments of the Z statistics (i.e., the Wald statistics constructed using model-based treatment effect estimates) of the 2 stages are combined by pre-specified weights that are based on the planned proportion of total number of subjects at which the interim analysis would be taken if there were no change in the design.

In the present case, the study is designed for 165 subjects with an interim analysis after approximately 76 subjects are evaluated for the primary efficacy endpoint. Therefore, the planned proportions are 0.46 and 0.54 for the two stages, respectively. The independent incremental Z statistics for the 2 stages are combined with weights that equal the square root of 0.46 for Stage 1 and square root of 0.54 for Stage 2. Hypothesis test of the null hypothesis  $H_0: \delta \leq 0$ , tested at one-sided 2.5% level at final analysis, is based on the CHW test statistic,  $Z_{CHW}$ , which combines the independent stage-wise test statistics defined in Section 5.1, as follows:

$$Z_{CHW} = \sqrt{w} Z_1 + \sqrt{1-w} Z_2.$$

The p-value is defined by  $P_{CHW} = \Phi(Z_{CHW})$ , where  $\Phi$  is the cumulative probability based on standard normal distribution. Gao et al (2008) have shown that the type-1 error is preserved at the specified  $\alpha$  level despite the possibility of a data-dependent increase in the sample size.

If the total sample size is not increased in a data-dependent manner as a result of the interim analysis, the primary analysis of the primary endpoint will be performed using the conventional test statistic generated from an ANCOVA model (as described in Section 9.2.1) to determine if statistical significance is reached. As a sensitivity analysis, the CHW test statistic will be computed as described above.

All sensitivity and supplementary analyses outlined in Sections 9.3.3 and 9.3.4 will use the same method (ie, CHW test statistic or conventional test statistic) as the primary analysis of the primary endpoint.

Statistical significance for the treatment comparison will be determined using the multiple comparison procedure described in Section 9.1. Descriptive statistics and LS means for the percent change from baseline in total glucocorticoid daily dose (with androstenedione control) at Week 24 will be presented by treatment group along with the LS-mean treatment difference, 95% confidence intervals, and p-value.

Descriptive statistics will be presented by treatment group for the glucocorticoid total daily dose ( $\text{mg}/\text{m}^2/\text{day}$ ) observed, change from baseline, and percent change from baseline values at baseline (observed data) and each postbaseline visit. Mean ( $\pm \text{SEM}$ ) values of the glucocorticoid total daily dose at each visit will be summarized in line graphs by treatment group. Similar graphs will be presented for the change from baseline and percent change from baseline. These summaries will be presented for both the glucocorticoid total daily doses *without* the derivation of 0 for loss of androstenedione control as well as the glucocorticoid total daily doses *with* the derivation of 0 for loss of androstenedione control (for change from baseline and percent change from baseline summaries only).

The analyses described in this section for the primary efficacy endpoint will be repeated for the full analysis set excluding site number 1083.

